2037 2038 2039	This Ancillary Study will assess the safety of using the study system during exercise and meal bolus-related challenges. Outcome data are expected to be used to support regulatory filings for the device system.
2040	15.2 Sample Size
2041 2042 2043	Participation in the Ancillary Study will be offered to participants who are currently in the Extension Phase of the main study. The goal for sample size is to have 30-40 individuals participate in the Ancillary Study.
2044	15.3 Eligibility Criteria
2045 2046 2047	Participants must be currently in the Extension Phase of the main study, with at least 2 weeks and no more than 11 weeks completed to ensure sufficient comfort with the study pump and sufficient time to complete the protocol below.
2048 2049	Inclusion in the Ancillary Study requires investigator judgment that it is safe for the individual to participate.
2050	15.4 Study Procedures
2051 2052	On the day of enrollment into the Ancillary Study, informed consent will be obtained from interested participants, and eligibility will be verified.
2053 2054 2055	A paper logbook will be provided to participants that includes a page to record details about each challenge and procedural instructions about how participants will conduct these challenges. This material will be reviewed with each participant.
2056 2057 2058 2059 2060 2061	During home use, each participant will perform 3 exercise and meal bolus-related challenges (details below) appropriate for the age of the participant. Each challenge will be separated from the other challenges by at least 48 hours. Before starting each challenge, caregivers of the child must assure the child has a working CGM and Control-IQ is active. If activity is paused during an exercise-related challenge, the challenge may be continued to allow for continuation of the activity if the participant is able and willing to continue.
2062 2063	Participants will receive a guidance document for performing the challenges that includes the following safety mitigations:
2064 2065 2066	• The participant's parent or guardian must remain with the child at all times and monitor CGM readings frequently during and for at least two hours after completion of each challenge.

- The hyperglycemia safety protocol described in section 8.2.4 will be followed during each challenge.
 - The parent/guardian must have an on-call phone number for the study team prior to initiation of each challenge.

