- 2102 timing and carb amount, the actual stop and start time of exercise, any associated hypoglycemia
- treatments, and any additional snacks given will be recorded on a study exercise log.

- 2104 Exercise Challenge: At least 2 hours after the child finishes an afternoon meal, a
- 2105 parent/guardian will try to keep the child physically active (walking, running, playing) for at
- least 30 minutes if possible, or longer if desired. This can be mixed with mild activity. The 2106
- 2107 pump's Exercise Activity setting will be turned on 90 minutes after completion of the meal. The
- meal timing and carb amount of the last meal prior to exercise, the actual start and stop time of 2108
- 2109 exercise, any associated hypoglycemia treatments, and any additional snacks given will be
- 2110 recorded on a study exercise log.
- 2111 A challenge may be stopped for any reason, including participant non-cooperation, or concern
- 2112 for hypoglycemia, or repeated hypoglycemia.
- 2113 15.5 Outcomes and Analysis Plan
- 2114 A separate statistical analysis plan will be written for the Ancillary Study.
- 2115 Outcomes will include the following:
- 2116 **Key Safety Outcomes:**
- 2117 Severe hypoglycemia
- 2118 • Other adverse events
- 2119 All adverse events will be listed. Listings will include Participant ID, the event, whether the
- 2120 event was serious, whether the event was related to the study device, the event outcome, and a
- 2121 description of the event.
- 2123 **Other Outcomes**

- 2124 CGM-measured % <54 mg/dL overnight (all challenge types)
- 2125 • CGM-measured % <70 mg/dL overnight (all challenge types)
- 2126 • CGM-measured % >180 mg/dL overnight (all challenge types)
- 2127 CGM-measured % <54 mg/dL during the two hours immediately following the start of exercise for each exercise-related challenge 2128
- 2129 • CGM-measured % <70 mg/dL during the two hours immediately following the start of 2130 exercise for each exercise-related challenge
- 2131 • CGM-measured % >180 mg/dL during the four hours following the announced meal, or 2132 until the next meal bolus is given, for the missed meal bolus challenge
- 2133 CGM-measured % >300 mg/dL during the four hours following the announced meal, or 2134 until the next meal bolus is given, for the missed meal bolus challenge
- 2135 The percentage of time spent below 54 mg/dL from 10 PM - 5.59 AM the night of an exercise

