- 2136 challenge will be compared with percentage of time spent below 54 mg/dL the previous night
- using a linear mixed effects regression model. A point estimate, 95% confidence interval and 2137
- 2138 two-sided p-value will be reported for the challenge effect based on the linear regression model
- 2139 and a 5% level will be used to declare statistical significance. Residual values will be examined
- 2140 for an approximate normal distribution. If values are highly skewed, then robust regression using
- 2141 M-estimation will be used instead. Analysis of the percentage of time spent below 70 mg/dL 10

2142 PM – 5:59 AM the night of an exercise challenge will be performed in the same manner.

2143

- 2144 The percentage of time spent above 180 mg/dL from 10 PM - 5.59 AM the night of a missed
- meal bolus challenge will be compared with percentage of time spent above 180 mg/dL the 2145
- 2146 previous night using a linear mixed effects regression model. A point estimate, 95% confidence
- 2147 interval and two-sided p-value will be reported for the challenge effect based on the linear
- 2148 regression model and a 5% level will be used to declare statistical significance. Residual values
- will be examined for an approximate normal distribution. If values are highly skewed, then 2149
- 2150 robust regression using M-estimation will be used instead. Analysis of the percentage of time
- 2151 spent above 300 mg/dL 10 PM – 5:59 AM the night of a missed meal bolus challenge will be
- performed in the same manner. 2152

2153

- 2154 CGM-measured % <54 mg/dL during the two hours immediately following the start of exercise
- 2155 for each exercise challenge will be compared between the two exercise challenge groups using a
- 2156 paired t-test. CGM-measured % <70 mg/dL during this same period will be analyzed in the same
- 2157 manner.

- 2159 For each challenge type, the mean, standard deviation, and range will be given for the outcomes
- 2160 listed above relevant to the challenge type. Summary statistics for the overnight periods
- preceding the challenges will be presented with summary statistics for each challenge type. 2161
- 2162 **Safety Monitoring**
- 2163 Safety oversight will be the same as for the main study, as described in Chapter 10:.

Chapter 16: References

- 2164
- 2165 1. Brown S, Kovatchev B, Raghinaru D, Lum JW, Buckingham BA, Kudva YC, Laffel LM,
- Levy CJ, Pinsker JE, Wadwa RP, Dassau E, Doyle FJ, Anderson SM, Church MM, Dadlani

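### The paired t-test for the two-hour exercise comparison drops any child with only one usable exercise challenge; the mixed model already used overnight would keep that child

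*Protocol*

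**What the plan says.** The ancillary study is described in Protocol chapter 15.

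- **Size (15.2):** "The goal for sample size is to have 30-40 individuals" take part. No power, SD or effect size is given.
- **Challenges (15.4):** "During home use, each participant will perform 3 exercise and meal bolus-related challenges". Two of the three involve exercise: full meal bolus plus exercise, and exercise alone. Each is separated from "the other challenges by at least 48 hours". No order is set.
- **Stopping (15.4):** "A challenge may be stopped for any reason, including participant non-cooperation, or concern" for hypoglycemia, or repeated hypoglycemia.
- **Two-hour comparison (15.5):** "CGM-measured % <54 mg/dL during the two hours immediately following the start of exercise" "for each exercise challenge will be compared between the two exercise challenge groups using a" "paired t-test. CGM-measured % <70 mg/dL during this same period will be analyzed in the same" manner.
- **Overnight comparisons (15.5):** the night of a challenge is compared with the previous night "using a linear mixed effects regression model. A point estimate, 95% confidence interval and" a two-sided p-value.
- **Description (15.5):** mean, SD and range are given for each challenge type, and every adverse event is listed.

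Section 15.5 has no rule for a child with one usable exercise challenge. It promises a separate SAP for the ancillary study, which is not among the documents. The SAP supplied covers only the RCT phase (its section 17.2 and the note to its study design), so its missing-data rules do not reach this comparison.

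**The concern.** The two exercise challenges are separate home occasions, so a child can do one and not the other. The protocol itself leaves several routes to that:

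- Participation is voluntary (section 11.8).
- An exercise challenge has CGM start conditions (15.4).
- Entry is allowed with up to 11 weeks of the 13-week Extension Phase completed (15.3), which can leave little time to reschedule.
- Control-IQ must be active for a challenge (15.4). After a severe hypoglycemia event, continued pump use needs the agreement of the investigator, the Medical Monitor and the DSMB (10.6.1).

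Some of these routes depend on the glucose result of the first challenge. The complete pairs are then a selected group, and the contrast between the two challenges is estimated in that group only. The value measured in the one-challenge child is available but unused. Section 15.1 expects the outcome data to support regulatory filings, and the sample is small.

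**Working it through.** The plan gives no figure to reproduce here. It states no power, SD, skip rate or order for the ancillary study, so everything below beyond the sample size is an assumption.

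**1. Precision when the loss is unrelated to the outcome.** With n pairs and a two-sided 5% level (assumed, since 15.5 states a level only for the overnight models), the detectable difference d, in SDs of the within-child difference, solves P(T > t(0.975, n−1)) = 0.80. Here T is noncentral t with n−1 degrees of freedom and noncentrality d√n.

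| Children | One challenge only | Pairs left | Detectable d |
|---|---|---|---|
| 30 | 0% / 10% / 20% / 30% | 30 / 27 / 24 / 21 | 0.53 / 0.56 / 0.60 / 0.64 |
| 40 | 0% / 10% / 20% / 30% | 40 / 36 / 32 / 28 | 0.45 / 0.48 / 0.51 / 0.55 |

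**2. Bias when lows in the first challenge lead to skipping the second, full-bolus first.** Assume % <70 is a normal variable with SD 8, cut off at 0, with underlying means 4 (full-bolus) and 0 (exercise-only). The within-child correlation is 0.3 to 0.6.

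- Full-bolus mean: 4Φ(0.5) + 8φ(0.5) = 5.6.
- Exercise-only mean: 8φ(0) = 3.2.
- True difference: 2.4 points.
- Share with at least 10% low time in the first challenge: 1 − Φ(0.75) = 0.23.
- These children skip the second challenge with probability s, the others with probability 0.03. Overall missing is 0.227s + 0.773 × 0.03, that is 7%, 11% and 16% for s = 20%, 40% and 60%.

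| s | First-challenge mean, retained children | Complete-pair difference | Likelihood estimate, all observed challenges |
|---|---|---|---|
| 3% (no dependence) | 5.6 | 2.4 | 2.4 |
| 20% | 5.2 | 2.1–2.2 | 2.4 |
| 40% | 4.7 | 1.7–1.9 | 2.4 |
| 60% | 4.2 | 1.3–1.6 | 2.4 |

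The first-challenge mean falls by up to 5.6 − 4.2 = 1.4 points. The second-challenge mean among the same children falls by less, because the correlation is below 1, so the difference shrinks.

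**3. Dependence on order.** A second simulation used 35 children, with lows in 40% of full-bolus and 25% of exercise-only windows, a true difference of about 3.2 points, and 30% to 50% skipping after a low.

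| Order | Complete-pair estimate |
|---|---|
| Full-bolus first | 2.1 down to 1.1 |
| Exercise-only first | 3.8 up to 4.4 |
| Random | off by about 0.2 to 0.4 |

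A random-intercept model on all observed challenges gave 2.8 to 3.1. That is closer to 3.2 than the complete pairs under either fixed order, though not exact. With 5% loss unrelated to the outcome, the two methods agreed.

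**The case against.** Several stronger readings are tempting, and the documents do not support them.

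- **That this is the only formal test of lows around exercise.** It is the only formal test of the two-hour window. The overnight comparisons also test time below 54 and 70 mg/dL after exercise, by mixed model.
- **That lows disappear from the report.** The per-challenge summaries do not require pairing, all adverse events are listed, and severe hypoglycemia is a key safety outcome. Only the contrast between the two challenges is affected, and that contrast does not measure how often lows occur.
- **That stopping a challenge early removes the child.** The window runs from the start of exercise, so a stopped challenge can still give a value. The loss needs a challenge that was never started or lacks usable CGM data.
- **That the difference is necessarily understated.** That follows only if full-bolus comes first. The reverse order overstates it, and with a mixed order the two largely cancel. A similar simulation put the bias at 10% skipping at no more than 0.2 points in any order, against a sampling SD of about 2.2 points for the paired estimate.

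It is also fair to say that each child is expected to do all three challenges, that no passage describes skipping a second challenge after a low, and that a paired t-test is a standard choice for a within-child contrast. These comparisons are listed under Other Outcomes in an optional study with no power claim, and the separate ancillary SAP may already deal with one-challenge children.

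What remains is that the test named in 15.5 excludes such children, and nothing in the documents supplied changes that.

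**Conclusion.** The point holds in a limited form and is optional to minor. The stated paired t-test discards observed two-hour values from children with one usable exercise challenge. The loss of precision needs only that such children exist: with 10% to 30% of them, the detectable difference rises by 0.03 to 0.11 SDs. Bias needs more, namely skipping that depends on lows in the first challenge and an order that is mostly one way.

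In the assumed scenarios with full-bolus first, a true difference of 2.4 points becomes 1.3 to 2.2, and one of about 3.2 becomes 1.1 to 2.1. With exercise-only first, about 3.2 becomes 3.8 to 4.4. With a random order the error is a few tenths of a point. None of these is a prediction, because the documents give neither a skip rate nor an order.

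**What to change.** In Protocol section 15.5 and the ancillary SAP:

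- Make the two-hour comparison of time below 54 and below 70 mg/dL with a linear mixed model, as for the overnight outcomes. Use challenge type as a fixed effect and child as a random effect, and include every started exercise challenge with usable CGM data.
- Report how many children contributed one and two exercise challenges, and why the other is missing.
- Keep the complete-pair t-test as a check.

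The cost is a sentence or two of text and no new data. With complete pairs the two analyses give essentially the same answer. The small downside is that the mixed model relies on missingness depending only on observed values, and on a normal model for skewed percentages. The overnight analyses already accept the same model, with robust regression as the stated fallback for high skew.

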Précis	A randomized controlled trial of at-home closed loop system vs. standard care (defined as either multiple daily injections of insulin [MDI] or use of an insulin pump without hybrid closed-loop control capabilities [low-glucose suspend or predictive low-glucose suspend functionality is permitted]) in youth age 2 to <6 years old.
Investigational Device	t:slim X2 with Control-IQ and Dexcom G6 system
Objectives	The objective of the study is to assess efficacy, quality of life, and safety of a closed loop control (CLC) system (t:slim X2 with Control-IQ Technology) in a randomized controlled trial with partial crossover.
Study Design ¹	First phase: a 13-week parallel group randomized clinical trial with 2:1 randomization to intervention with the closed loop system vs. standard care (SC); Second Phase: following the RCT, a 13-week period where the Standard Care (SC) group will transition to use CLC and the experimental arm will extend the use of CLC for the same period. After 26 weeks, participants may continue using CLC for an additional Extended Use period. A subset of participants will be invited to join an optional exercise/meal challenge ancillary study.
Number of Clinical Centers	~3 US clinical centers
Endpoints	Efficacy The primary outcome for the RCT is time in target range 70-180 mg/dL (TIR) measured by CGM in CLC group vs. SC group over 13 weeks The primary outcome for the extension phase assessed separately for each treatment group is change in TIR comparing extension phase with RCT phase.
	Quality of Life Patient-reported outcome questionnaires will be completed. Safety The key safety outcomes are severe hypoglycemia and ketoacidosis.
Population	 Inclusion Criteria Clinical diagnosis, based on investigator assessment, of type 1 diabetes for at least 6 months and using insulin for at least 6 months Familiarity and use of a carbohydrate ratio for meal boluses. Age ≥2 and <6 years old Living with one or more parent/legal guardian knowledgeable about emergency procedures for severe hypoglycemia and able to contact emergency services and study staff. Investigator has confidence that the parent can successfully operate all study devices and is capable of adhering to the protocol Willingness to switch to lispro (Humalog) or aspart (Novolog) if not using already, and to use no other insulin besides lispro (Humalog)

PARTICIPANT AREA	DESCRIPTION
	 or aspart (Novolog) during the study for participants using a study-provided Tandem pump during the study. 7. Total daily insulin dose (TDD) at least 5 U/day 8. Body weight at least 20 lbs 9. Willingness not to start any new non-insulin glucose-lowering agent during the course of the trial 10. Participant and parent(s)/guardian(s) willingness to participate in all training sessions as directed by study staff. 11. Parent/guardian proficient in reading and writing English 12. Live in the United States, with no plans to move outside the United States during the study period
	Exclusion Criteria
	 Concurrent use of any non-insulin glucose-lowering agent (including GLP-1 agonists, Symlin, DPP-4 inhibitors, SGLT-2 inhibitors, sulfonylureas). Hemophilia or any other bleeding disorder History of >1 severe hypoglycemic event with seizure or loss of consciousness in the last 3 months History of >1 DKA event in the last 6 months not related to illness, infusion set failure, or initial diagnosis History of chronic renal disease or currently on hemodialysis History of adrenal insufficiency Hypothyroidism that is not adequately treated Use of oral or injectable steroids within the last 8 weeks Known, ongoing adhesive intolerance Plans to receive blood transfusions or erythropoietin injections during the course of the study A condition, which in the opinion of the investigator or designee, would put the participant or study at risk Currently using any closed-loop system, or using an insulin pump that is incompatible with use of the study CGM Participation in another pharmaceutical or device trial at the time of enrollment or during the study Employed by, or having immediate family members employed by Tandem Diabetes Care, Inc., or having a direct supervisor at place of employment who is also directly involved in conducting the clinical trial (as a study investigator, coordinator, etc.); or having a first-degree relative who is directly involved in conducting the clinical trial
Sample Size	Up to 150 screened participants with the goal of randomizing 102 participants.
Treatment Groups	 Intervention Group: t:slim X2 with Control-IQ Technology and Study CGM. Control Group: Standard care (SC) - defined as either multiple daily injections of insulin (MDI) or use of an insulin pump without hybrid closed-loop control capabilities (low-glucose suspend or predictive low-glucose suspend functionality is permitted) in conjunction with study CGM All participants will be offered to extend the study for an additional 13 weeks, with the SC group switching to the t:slim X2 with Control-IQ System after the 13-week RCT period. After 26 weeks, participants may continue using CLC for an additional Extended Use period.

PARTICIPANT AREA	DESCRIPTION
Participant Duration	${\sim}26\text{-}32$ weeks for RCT and Extension Phase, depending on duration of run-in phase; up to an additional ${\sim}7$ months in Extended Use period
Protocol Overview/Synopsis	After consent is signed, eligibility will be assessed. Eligible participants not currently using an insulin pump and Dexcom G5 or Dexcom G6 CGM with minimum data requirements will initiate a run-in phase of 2 to 6 weeks that will be customized based on whether the participant is already a CGM user. Participants who skip or successfully complete the run-in will be randomly assigned 2:1 to an intervention using Tandem t:slim X2 with Control-IQ Technology or the standard care control group using existing insulin therapy in conjunction with study CGM. All participants will continue their participation by using the t:slim X2 with Control-IQ system in an Extension Phase. After 26 weeks, participants may continue using CLC for an additional Extended Use period through no later than July 31, 2022. A subset of participants will complete an optional exercise/meal challenge ancillary study.

¹ This SAP is restricted to the RCT Phase. Analyses of the Extension Phase, Extended Use Period, and Ancillary Study are specified in a separate SAP.

The following table provides an overview of the schedule of study visits, phone contacts, and key procedures. 48

49

Table 2. Schedule of Study Visits and Procedures During the RCT and Extension Phases¹ 50

	Pre	Pre	0	3d²	1w	2 w	6w	10w	13w	13w + 3d	14w	15w	19w	23w	26w
Visit (V), Videoconference (VC), or Phone (P)	VC/V	VC/V	VC/V	VC/ P	P	VC/ V	VC/ V	P	VC/ V	VC/ P	Ρ	VC/ V	VC/ V	P	VC/ V
Comment	Screen/ Enroll	Run-in	Rand												
Eligibility Assessment	X	X	X												
HbA1c (Central lab)			X						X						X
Device Data download(s)	X	X	X	X	X	X	X	X	X	X	X	X	X	X	X
Review diabetes management and AEs		X	X	X	X	X	X	X	X	X	X	X	X	X	X
Questionnaires as defined in section 9.2 of the Protocol	х								X						X
51 ¹ This SAP is res	stricted to t	he RCT pha	se. Analysi	es of the	Extensio	on phase	are spe	cified in	a separc	ite SAP.					

52

² Only for participants on MDI at enrollment assigned to the CLC group

53 54

PEDAP SAP v3.1

Page 7 of 21

55 **2.** Comparison with the Protocol

This SAP is consistent with version 11.0 of the protocol except for the following: 56 The Hypoglycemia Confidence Scale and System Usability Scale have been added to the 57 list of questionnaires in Section 5.2.2. 58 59 • Changed sensitivity analysis in Section 6.3 to include all hierarchical outcomes instead of 60 just % in range 70-180 mg/dL. 61 • A sensitivity analysis including CGM data after the 13-week visit has been added (Section 6.3). 62 • Exploratory analyses that require pre-randomization pump data have been removed. 63 64 3. Primary Statistical Hypotheses 65 The primary outcome for this study is CGM-measured % in range 70-180 mg/dL over a 13-week 66 period. The intervention will be considered effective if the Closed-Loop Control [CLC] is 67 superior to Standard Care [SC] using a statistical significance of α =0.05 and the model specified 68 69 below in Section 7 (i.e., p < 0.05). 70 The null/alternative hypotheses are: a. Null Hypothesis: There is no difference in mean CGM-measured % in range 70-180 71 mg/dL over 13 weeks between SC and CLC 72 b. Alternative Hypothesis: The mean CGM-measured % in range 70-180 mg/dL over 13 73 weeks is different for SC and CLC. 74 75 76 4. Sample size Based on data from the DCLP5 study (Breton et al.), we conservatively estimate the standard 77 78 deviation (SD) for the primary outcome, time in range (TIR), to be 10%. A sample size of N=90 79 subjects (60 in the CLC arm and 30 in the SC arm) therefore will give 90% power to detect a 7.5% improvement in TIR with a two-sided test and type 1 error of 5%. Accounting for potential attrition 80 81 rate of up to 10%, the total sample size for the PEDAP Study is estimated at N=102. 82 The following table shows the minimum detectable difference with a total sample size N=90 for 83 key secondary outcomes. The observed standard deviations are taken from the DCLP5 study. 84

	Sta	ndard Devia	ation	Correlation		Detectable
	CLC	SC	Pooled	with	Effective	Difference
Outcome	(n=78)	(N=22)	(N=100)	Baseline	SD ^a	with N=90 ^b

% >250 mg/dL ^c	5.5%	9.9%	6.5%	0.69	4.7%	3.4%
Mean Glucose ^d	18	26	20	0.68	14	10
HbA1c	0.8%	0.9%	0.8%	0.70	0.6%	0.4%
% <70 mg/dL $^{\rm c}$	1.07%	1.13%	1.08%	0.61	0.86%	0.63%
% <54 mg/dL $^{\circ}$	0.23%	0.23%	0.23%	0.54	0.19%	0.14%

85 a – After accounting for the baseline value as a covariate in the regression model.

86 b – With 90% power and two-sided type 1 error rate = 5%.

87 c – Outcomes with a skewed distribution winsorized at the 10th and 90th percentiles.

88 d – Units for mean glucose are mg/dL

89 5. Outcome Measures

90 5.1. Primary Efficacy Outcome

• The primary outcome is CGM-measured % in range 70-180 mg/dL

92 **5.2. Secondary Efficacy Outcomes**

93 **5.2.1.** Hierarchical Outcomes

The following secondary outcomes will be tested in a hierarchical fashion between the interventionarms as described in Section 7.2.1.

- CGM-measured % above 250 mg/dL
- CGM-measured mean glucose
- HbA1c at 13 weeks
- CGM-measured % below 70 mg/dL
- CGM-measured % below 54 mg/dL
- 101 102

105

107

112

